## 2.4 Interim Analyses

No formal interim analysis is planned for this study. However, data collected up through the first 24 hours post procedure may be analyzed prior to all subjects completing this time point. This data may be used for publications and/or marketing purposes, but will not be used to change the study design or procedures. The study will continue as planned until the required sample size has been enrolled.

Additionally, once all subjects have completed the six month follow up visit, the data collected up through that visit may be analyzed. Data from the 12 month follow up visit will not be analyzed until all subjects complete the study.

Separate Interim Data Review Plan (IDRP) documents will be written to describe the procedures for performing the data reviews at 24 hours and six months post procedure.

## 2.5 Study Center Considerations in the Data Analysis

A study center is defined as a treatment administration site or group of treatment administration sites under the control and supervision of the same Principal Investigator (PI). There will be no selective pooling of study centers.

## 2.6 Documentation and Other Considerations

The data analyses will be conducted using SAS© Software, version 9.4 or later.

## 3.0 Analysis of Baseline Patient Characteristics

Baseline and demographic characteristics, including a detailed arrhythmia history, will be summarized for all subjects in the safety population. Continuous variables will be summarized via mean, standard deviation, median, range, and number of non-missing responses. Categorical variables will be summarized via counts and percentages.

Time-to-event (e.g., Time since first documented AF diagnosis) will be computed as

$$\text{TTE} = \text{End-Date} - \text{Start-Date},$$

where TTE represents the time to the event, End-Date the ending date for the event, and Start-Date the starting date for the event.

## 4.0 Analysis of Safety

### 4.1 Description of Safety Objectives

#### 4.1.1 Primary Safety Objective

The primary measurable objective is an analysis of the proportion of subjects who are free from device/procedure related Major Adverse Events (MAEs), as adjudicated by the Clinical Events Committee (CEC), that occur within the first 24 hours post index procedure. MAEs include any of the following:

- Death
- Cardiac perforation/tamponade
- Cerebral infarct, transient ischemic attack (TIA), or systemic embolism
- Major bleeding
- Mitral or tricuspid valvular damage
- Other serious adverse device effects (SADEs) adjudicated by an independent CEC as “probably related” to the AcQMap System

#### 4.1.2 Secondary Safety Objectives

The secondary safety analysis measures are defined as follows:

- All adverse events (AEs) reported through 12 months
- 12-lead ECGs and Holter monitor results
- Physical exam findings
- Vital signs

#### 4.2 Analysis of Safety Objectives

##### 4.2.1 Analysis of Primary Safety Objective

Subjects who remain free from device/procedure related MAEs, as adjudicated by the CEC, that occur within the first twenty-four (24) hours post index procedure will be considered a success with respect to the primary safety objective, and subjects who experience at least one such MAE will be considered a primary safety failure. MAEs that occur during the first 24 hours will be reported and adjudicated by the CEC for any probable relationship to the device and/or procedure.

The analysis of the primary safety objective will be performed on the safety population. The number and proportion of subjects in the safety population who are primary safety successes will be computed, along with a 95% exact binomial (i.e., Clopper-Pearson) confidence interval on the proportion.

##### 4.2.2 Analysis of Secondary Safety Objectives

With the exception of treatment emergent adverse events (TEAEs), all analysis of secondary safety objectives will be conducted on the treatment population. TEAE analyses will be conducted on the safety population.

#### Adverse Events

All treatment-emergent AEs (TEAEs) occurring during the study will be recorded and classified on the basis of the Medical Dictionary for Regulatory Activities (MedDRA®) terminology. Treatment-emergent AEs are those AEs with an onset on or after the start time of the ablation procedure (defined as the point the AcQMap catheter is deployed in the left atrium). All TEAEs will be categorized by the number of subjects reporting the TEAE, severity, device relationship as adjudicated by the CEC (not related, possibly related, probably related, and definitely related), procedure relationship as adjudicated by the CEC (not related, possibly related, probably related, and definitely related), and seriousness. A separate relationship table will be provided for each device in the study (AcQMap System, AcQGuide Sheath, AcQMap Catheter, and Patient Electrode Kit).

A separate TEAE summary table will be constructed to display the number of TEAEs, the number of subjects with at least one TEAE, the maximum severity per subject, the maximum device relationship per subject, the maximum procedure relationship per subject, the number of subjects experiencing at least one serious TEAE, the number of withdrawals from the study due to a TEAE, and the number of deaths.

The device and procedure relationships used in the analysis tables will be based on the CEC adjudicated results. However, the relationships assigned by the investigators will be listed. TEAE adjudicated as non-events by the CEC will not be analyzed.

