##### Safety Outcome Measure

- Recording and analysis of all identified adverse events (AEs) and adverse device effects (ADEs) through 12 months post-procedure. Events will be adjudicated by an independent Clinical Events Committee (CEC) for severity and relationship to the AcQMap

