**Figure 1: Ablation Procedure Flow Diagram**

### **7.3.2 Procedure Data Collection**

Collection of data generated during the procedure should include:

- Medications and any change in health prior to the ablation
- Recording of 12 lead ECG at procedure start
- Recording of 12 lead ECG at procedure completion
- Total procedure time (from first venous access to study completion)
- Total fluoroscopy time and times to complete segments of the ablation procedure
- Ablation time to complete PVI (delineate RF vs Cryo)
- Ablation time for additional LA lesions (separate AF from AT ablations)
- Ablation times for right atrial ablations
- Recording of all DCCV used during the procedure
- EP recording of all atrial tachyarrhythmias noted during the procedure
- EP recording of conversion to sinus rhythm (either spontaneous or DCCV)
- EP recording demonstrating PV isolation of all treated veins
- Recording of any right atrial arrhythmias mapped and/or treated
- Recording of all AADs infused during the procedure
- Recording of any medications administered for anticoagulation reversal

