## 9 ADVERSE EVENTS

For the purpose of this protocol, an adverse event is any untoward medical occurrence, unintended disease or injury, or any untoward clinical signs in subjects whether or not related to the AcQMap System, and includes events related to the procedures involved

in the clinical investigation plan. Any adverse event (AE) that occurs in a subject once they are considered a “safety” population is considered an AE. Any medical conditions, problems, signs, symptoms, and findings occurring prior to enrollment are to be reported as pre-existing conditions on the Medical History eCRF.

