## 2.2 Analysis Populations

The following analysis populations will be defined for the study:

**Safety Population** – The safety population will include all enrolled subjects who have the venous access portion of the ablation procedure initiated.

**Treatment Population** – The treatment population will include all enrolled subjects who complete a procedure up to the point the AcQMap catheter has completed mapping the atrial anatomy.

The analysis of the primary safety objective of the study will be based on the safety population. The analysis of the secondary safety and effectiveness outcomes will be based on the safety population or the treatment population as indicated in Sections 4 and 5 below.

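### The SAP tabulates treatment-emergent AEs for everyone from venous access but counts AEs only from left-atrial catheter deployment, so earlier AEs are left out

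*Combined protocol and SAP*

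**What the plan says.** SAP 4.2.2 states that "TEAE analyses will be conducted on the safety population". SAP 2.2 defines that population as enrolled subjects who "have the venous access portion of the ablation procedure initiated". Under Adverse Events, SAP 4.2.2 defines a TEAE as an AE with "onset on or after the start time of the ablation procedure (defined as the point the AcQMap catheter is deployed in the left atrium". The AE outputs described there are all TEAE outputs: breakdowns by severity, seriousness, device relationship and procedure relationship, a relationship table for each of four devices (System, Sheath, Catheter, Patient Electrode Kit), and one summary table.

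The protocol starts earlier. Section 9 opens its rule with "Any adverse event (AE) that occurs in a subject once they are considered a" and then names the safety population, so collection begins at venous access. The secondary safety measure in section 6.2.2 is "Recording and analysis of all identified adverse events (AEs) and adverse device effects (ADEs) through 12 months post-procedure", and SAP 4.1.2 likewise lists all AEs reported through 12 months. Section 6.5 treats venous access as part of the ablation procedure and follows subjects who do not complete the AcQMap procedure for AEs until discharge. Section 7.3.2 times the procedure from the same point: "Total procedure time (from first venous access to study completion".

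**The concern.** The population and the event definition use different clocks. A subject enters the TEAE analysis at venous access, but that subject's AEs begin to count only at left-atrial deployment. AEs that the protocol collects in that interval have no place in the AE summaries that the SAP describes.

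The sheath is the clearest case. Protocol 5.4.4 explains that it is placed in the chamber so that the catheter can then be introduced and deployed. An AE caused by the sheath before that moment would be missing from the sheath's own relationship table.

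There is also a reconciliation problem. The primary analysis in SAP 4.2.1 uses the safety population and does not refer to the TEAE definition. A related cardiac perforation before deployment could therefore make a subject a primary safety failure yet be absent from the count of subjects with a serious TEAE.

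**Working it through.** The plan gives no figure for this point, so the check compares definitions and counts the outputs affected.

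1. **The two start points.** Let V be initiation of venous access and D be left-atrial deployment of the catheter, with V before D.
   - Protocol section 9: an AE counts if onset ≥ V.
   - SAP 4.2.2: a TEAE requires onset ≥ D.
   - AEs lost in deployed subjects: V ≤ onset < D.
   - Never-deployed subjects: D does not exist, so the condition onset ≥ D cannot be met. Their AEs up to discharge do not satisfy the definition.

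2. **Direction.** Every AE with onset ≥ D also has onset ≥ V. The TEAE set under the SAP rule is therefore contained in the set under the protocol rule. Numbers of events, numbers of subjects with an event, and the maximum severity or relationship per subject can stay the same or fall. None can rise.

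3. **Outputs affected.** Four device-relationship tables plus one summary table gives at least 5. The summary table lists eight measures: number of TEAEs, subjects with a TEAE, maximum severity, maximum device relationship, maximum procedure relationship, subjects with a serious TEAE, withdrawals due to a TEAE, and deaths. Seven depend on the onset rule; deaths do not.

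4. **Which AEs could fall in the gap.** Protocol 10.1 lists AV fistula, pseudoaneurysm, local hematoma, vascular bleeding, vasovagal reaction and anesthesia reaction. That access or sedation can cause these before deployment is clinical judgement; the list gives no timing. An access-site event first seen after deployment still counts.

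5. **Size.** The documents contain no rate of stopped procedures or early AEs. As scale only, assume a safety population of 125 and a table that reports percentages. Each subject whose only AE falls in the gap then moves the proportion with at least one TEAE by 1/125 = 0.8 percentage points. An assumed 1 to 10 such subjects would move it by 0.8 to 8.0 points (10/125 = 8.0%). These counts are not estimates.

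6. **Primary analysis.** The precision statement in SAP 1.3 reproduces. With 120 of 125 subjects free of MAEs (96.0%), the Clopper-Pearson limits are 90.91% and 98.69%, and (98.69 − 90.91)/2 = 3.89%. Nothing in that calculation or in SAP 4.2.1 depends on the TEAE definition, so it does not change.

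**The case against.** Several counter-arguments carry weight.

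- **Never-deployed subjects are not expressly excluded.** The SAP gives them no start time and no rule. Since SAP 4.1.2 promises all AEs and the TEAE population is the safety population, a programmer might include their events. That stands: the handling is undefined rather than a stated exclusion. It does not help deployed subjects, for whom the rule is explicit.
- **Practice may be more lenient than the text.** Protocol 7.3.2 does not explicitly list a deployment clock time, and the SAP's elapsed-time conventions use dates. Every procedure-day AE might be flagged as treatment-emergent. The SAP does not say so, and the outcome should not depend on an unwritten choice.
- **Deployment marks exposure to the mapping catheter.** That could justify a catheter-only table. It does not fit tables that also report procedure relationship and a separate sheath relationship.
- **The reach is limited.** These are secondary, descriptive tables with no hypothesis tests. The SAP revision history refers to an AE listing (Listing 6). The documents do not say whether it is limited to TEAEs, so it may still show the events.

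A reader might extend the criticism to the exam, vital-sign and ECG tables, because SAP 4.2.2 says "With the exception of treatment emergent adverse events (TEAEs), all analysis of secondary safety objectives will be conducted on the treatment population", and SAP 2.2 requires those subjects to "complete a procedure up to the point the AcQMap catheter has completed mapping the atrial anatomy". The documents do not support calling that an error. The revision history records the mapping-based definition as a deliberate change. Subjects who do not complete the AcQMap procedure are followed only for AEs, up to discharge. Moving 12-lead ECG to the safety population would mix populations within the rhythm results, since SAP 2.3 fills missing Holter data from 12-lead ECG. It would also require identifying un-ablated subjects, for whom the SAP defines no flag. Protocol 6.5 does follow deployed subjects for the full study, so one without completed mapping would be followed yet absent from these tables. That is a trade-off, and no document shows that such a subject exists.

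**Conclusion.** The TEAE onset rule is wrong as written. It starts later than the population it is applied to and later than the protocol's own rule for counting AEs, and no other text repairs it. The consequence is one-sided: AE counts in at least five secondary outputs can be too low. The amount is unknown and may be small. The conclusion rests on a literal reading of the definition and on the clinical judgement that some AEs begin between venous access and deployment.

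Three stronger inferences are tempting and should not be drawn:

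- **That the primary safety result is biased.** SAP 4.2.1 does not use the TEAE definition, so related MAEs within 24 hours still count there.
- **That TEAE percentages are diluted by subjects who cannot have an event.** The text describes counts and states no percentage or denominator, and the table shells are not available.
- **That AE reporting is materially understated.** No rate in the documents supports a size.

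**What to change.** Replace the TEAE onset definition in SAP 4.2.2 with: 'A treatment-emergent AE is any AE whose onset is at or after initiation of venous access for the index ablation procedure; an AE dated on the procedure day with no onset time is treated as treatment-emergent.'

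The cost is one text change and the matching analysis flag. No new data are needed: these AEs are already reportable under the protocol, and first venous access already starts the procedure-time measure. The clause on missing onset times may admit an occasional procedure-day event that began before access, which is the cautious direction for a safety table.

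The small downside is that access-related events unrelated to mapping will enter the TEAE tables. The CEC device- and procedure-relationship categories already planned will separate them. Leave the populations for the exam, vital-sign, ECG and Holter summaries unchanged.

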## **6.5 Clinical Study Enrollment Definitions**

For the purposes of this clinical study, the following definitions regarding the status of a subject will apply:

Screen Failure Subject – Any subject who has not met all of the inclusion and exclusion criteria. This includes a subject who may be excluded based on the results of the pre-procedure TEE. Screen failure subjects should have the screening eCRF completed and the screening data entered in the database.

Enrolled Subject – Any subject who has signed an informed consent form and is deemed study eligible by meeting all of the inclusion and exclusion criteria.

Pre-treatment Subject – Any enrolled subject who has the venous access portion of the ablation procedure initiated. Pre-treatment patients that do not complete the AcQMap procedure will be followed for adverse events through hospital discharge. In addition to the discharge eCRF, a study completion eCRF will be completed. No follow-up beyond the hospital discharge will be required.

Treatment Subject – Any pre-treatment subject who completes the ablation procedure to the point the AcQMap catheter and AcQGuide sheath has been deployed in the left atrium. Treatment subjects will be followed for all study outcome measures for the full duration of the clinical study. The number of treatment subjects will be used for the study sample.

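### The SAP starts TEAEs at left-atrial deployment of the AcQMap catheter but analyses them on a population that starts at venous access, so adverse events between the two drop out of the TEAE summaries

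*Combined protocol and SAP*

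**What the plan says.** **When a TEAE can begin.** SAP 4.2.2 (Adverse Events) requires onset at or after the "start time of the ablation procedure (defined as the point the AcQMap catheter is deployed in the left atrium".

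**Who is analysed.** SAP 4.2.2 states that "TEAE analyses will be conducted on the safety population". SAP 2.2 defines that group, in the same words as protocol 8.1: "The safety population will include all enrolled subjects who have the venous access portion of the ablation procedure initiated".

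**When the protocol starts counting.** Protocol section 9 ties the adverse event definition to entry into the safety population ("Any adverse event (AE) that occurs in a subject once they are considered a" member of that population). Protocol 7.3.2 measures the procedure from the same point: "Total procedure time (from first venous access to study completion".

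**Subjects who do not get as far as mapping.** Protocol 6.5 provides that "Pre-treatment patients that do not complete the AcQMap procedure will be followed for adverse events through hospital discharge".

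**What the safety objective is.** Protocol 6.2.2 lists "Recording and analysis of all identified adverse events (AEs) and adverse device effects (ADEs) through 12 months post-procedure", and SAP 4.1.2 lists "All adverse events (AEs) reported through 12 months". Neither is limited to treatment-emergent events. The only adverse event summaries described in the SAP text are the TEAE summaries in 4.2.2.

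**The concern.** The numerator and the denominator of the TEAE summaries use different time origins. The SAP is also inconsistent about when the procedure starts: section 2.2 treats venous access as part of the ablation procedure, while section 4.2.2 starts that procedure later, at deployment.

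The stage left out is part of the procedure under study, and the study objective covers procedure-related as well as device-related safety. SAP 4.2.2 promises relationship tables for the procedure and for each device, including the AcQGuide sheath. Protocol 5.4.4 describes the sheath as the route by which the catheter is introduced and deployed, so some of its use precedes the point at which counting begins. The serious-TEAE row uses the same filter. If events during the procedure count toward the primary endpoint, a major event before deployment could be a primary failure under SAP 4.2.1 and still be missing from the serious-TEAE row.

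**Working it through.** **1. The plan's own sizing figure.** SAP 1.3 and protocol 8.4 state 125 subjects and a 95% half-width of 3.89% at an observed 96.0%. The Clopper-Pearson interval for 120/125 is 90.91% to 98.69%, and (98.69 − 90.91)/2 = 3.89 percentage points. The figure reproduces. It concerns the primary endpoint and does not depend on the TEAE definition.

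**2. Applying the definitions to each type of event.**

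| Event | AE under protocol section 9? | Subject in TEAE denominator? | TEAE under SAP 4.2.2? |
|---|---|---|---|
| Onset at or after deployment | Yes | Yes | Yes |
| Onset after venous access, before deployment | Yes | Yes | No |
| Any onset after access, catheter never deployed | Yes | Yes | No: there is no start time |

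The last two rows are the events lost. The cut is by onset time, so an access-site, transseptal or sheath complication that begins after deployment is still counted.

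**3. Size, by assumption only.** The documents give no count of pre-deployment events and no count of never-deployed subjects. The denominator of 125 comes from SAP 1.3 and is itself an assumption here. Protocol 6.5 says that treatment subjects make up the study sample, so the safety population may be larger.

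*Subjects whose only event falls in the window.* With k such subjects, the summaries show 0% where the true figure is k/125: 1/125 = 0.8%, 2/125 = 1.6%, 3/125 = 2.4%.

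*The row for at least one TEAE.* If T subjects truly have an event and k are lost, the row shows (T − k)/125:

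| T (true rate) | k = 1 | k = 2 | k = 3 |
|---|---|---|---|
| 10 (8%) | 7.2% | 6.4% | 5.6% |
| 20 (16%) | 15.2% | 14.4% | 13.6% |
| 40 (32%) | 31.2% | 30.4% | 29.6% |

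*A single event type.* If 5 subjects are counted, the table shows 5/125 = 4.0%. With 3 more in the window, the full figure is 8/125 = 6.4%.

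*Never-deployed subjects.* If the rate among deployed subjects is 20% and u of 125 are never deployed, the reported rate is 0.20 × (125 − u)/125. For u = 2, 5 and 10 this is 19.7%, 19.2% and 18.4%.

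In every case the shift is downward.

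**The case against.** **The rule might be applied by date.** The SAP's other timing rules work in dates: date imputation in 2.3, End-Date minus Start-Date in 3.0, and the date format in Appendix A. Protocol 9.1 mentions time of onset in connection with serious and unanticipated events, so clock times may not exist for every event. If access and deployment fall on the same day, a date comparison would keep window events in deployed subjects. This is a fair point about what programmers might do. But the written rule refers to a start time, and a date comparison still gives never-deployed subjects no start point.

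**The events may appear elsewhere.** The SAP revision history mentions an adverse event listing and labels the related tables as AE tables. The table and listing shells are not in the supplied text, so this cannot be checked. A listing would in any case not be a summary, and no table of non-treatment-emergent events is described. One could read SAP 4.2.2 as sending such events to the treatment population, but that would still leave out never-deployed subjects.

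**Starting at first use of the mapping catheter is a possible design choice.** It is, but it then needs a matching population or a separate summary of the earlier phase. The SAP has neither.

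**The consequence is limited.** This stands. The primary analysis is unaffected, the SAP plans no hypothesis tests, and no stated decision rule uses a TEAE rate. The percentages above show direction and scale only; no figure in the documents shows that any event will fall in the window.

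**Conclusion.** The concern holds. As written, SAP 4.2.2 removes two groups of events from the TEAE numerator while keeping the subjects in the denominator: events between venous access and left-atrial deployment, and all events in never-deployed subjects. This conflicts with the SAP's own population definition, the protocol's adverse event definition and the objective of analysing all adverse events through 12 months.

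The size cannot be derived from the documents. Under the assumed counts, the overall row moves by 0.8 to 2.4 percentage points. That is modest for a common outcome, but large in relative terms for a rare event type. The conclusion rests on reading the start-time rule literally. It covers the summaries described in SAP 4.2.2 and makes no claim about listings. It should be fixed before analysis: the definition is wrong as written and under-reports safety events, although the main result does not turn on it.

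**What to change.** Replace the TEAE sentence in SAP 4.2.2 so that a TEAE is any adverse event with onset at or after initiation of venous access for the index procedure. This aligns it with SAP 2.2, protocol section 9 and the procedure start in protocol 7.3.2, and it gives never-deployed subjects a start point. State in the same place whether the comparison uses clock time or date, and how an event on the procedure day with no recorded time is classified. Check the table footnotes for the old definition.

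If the sponsor wishes to keep deployment as the TEAE start, the alternative is a separate summary, on the safety population, of all adverse events from venous access that the TEAE rule excludes, including those in never-deployed subjects.

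The cost is small: essentially one sentence and a changed reference time in the programs. No new data are needed, because the protocol already counts events from entry to the safety population and follows pre-treatment subjects to discharge. The one downside for the sponsor is that adverse event rates may look slightly less favourable.
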